3. DEMOGRAPHICS AND BASELINE ASSESSMENTS

The following are specific demographic / baseline assessments of interest for analyses. **Primary analyses will adjust for these covariates as we anticipate they will influence outcome.** We plan to report both model-adjusted and simple unadjusted intervention effect estimates:

- 1) Sex
- 2) Age
- 3) Keele STarT Back Screening Tool: a nine-item survey which assesses risk for progression to chronic base pain

Additional demographics and clinical characteristics we plan to collect and summarize (i.e., we **do not plan to include as covariates in analyses**) include:

- 1) Race / ethnicity
- 2) Education level
- 3) Marital status
- 4) Employment status
- 5) Activity level at work for those that are working at baseline
- 6) Income level
- 7) Physical activity level according to self-report
- 8) Nature of injury
- 9) Length of pain at baseline
- 10) Primary diagnosis
- 11) Medications administered / prescribed during initial ED visit

Note that some additional exploratory analyses may examine these additional variables as covariates and/or effect modifiers as well. We will label any exploratory analyses involving additional potential covariates as post hoc in any dissemination materials.

4. DATA STORAGE

Data will be collected and managed using Research Electronic Data Capture (REDCap) housed at Northwestern University's Clinical and Translational Sciences Institute (CTSA), NUCATS (1, 2) . REDCap is a secure, web-based application designed for research studies that provides an intuitive interface for validated data entry, audit trails for tracking data manipulation and export procedures, and automated export procedures for seamless data downloads to common statistical packages, and procedures for importing data from external sources. Individualized REDCap survey links will be sent to participants using Mosio, a secure text messaging research platform that is 21 CFR Part 11 compliant and integrates with REDCap.

5. RANDOMIZATION METHODS

We plan for equal allocation (1:1) of physicians across study arms; thus, there will be inevitable imbalance in patient numbers across study arms. Physicians will be randomized to either the intervention (NEED-PT) or "control" (usual care). Physicians randomized to the NEED-PT intervention will have a physical therapist assigned to their treatment team who will automatically evaluate all patients with low back pain. Physicians randomized to "usual care" will not have a physical therapist assigned to their treatment team, and their patients with low back pain will not be automatically evaluated by the physical therapist. Due to the inherent risk of cluster-level (i.e., physician-level) covariate imbalance between study arms in cluster-randomized trials, we will employ covariate-constrained randomization techniques to control for possible imbalance in key physician-level characteristics. Covariate-constrained randomization methods tend to ensure the most efficient

control over covariate imbalance between study arms at randomization (3, 4). With 40 total physicians, there are over 137 billion ways (40 choose 20) in which we can achieve equal allocation of physicians across study arms. The constrained randomization procedure will involve:

- 1) Enumerating a 10 thousand possible allocation schemes at the 1:1 physician allocation ratio.
- 2) Calculating imbalance in the following baseline physician-level variables across study arms for each of the schemes simulated in step 1:
 - a. Physician gender
 - b. Physician years' experience (since first year of residency)
 - c. Physician race
 - d. Physician opioid prescription rate
 - e. Number of "fast track" zone shifts for a physician per month, on average – fast track shifts are those with the highest likelihood of receiving low-back pain patients
 - i. This variable is highly correlated with the number of day shifts a physician tends to have per month
 - ii. It is also correlated with the mean number of patients the physician sees per hour
 - iii. While we will control imbalance in the randomization algorithm for this "fast track" zone variable, we anticipate reporting summary statistics on day shifts and patients per hour
- 3) Constraining the randomization space to a subset of allocation schemes that do not surpass some threshold of "allowable" imbalance for each of the variables (a-e in step 2) above. The thresholds will be guided by the following restrictions; however, the distribution of these physician-level variables may require modification(s) to these thresholds. Any updates will be documented in a later version of this SAP:
 - a. Physician gender counts may not differ by more than two for any one category across study arms.
 - b. Mean number of years' experience may not differ more than one year.
 - c. Physician race will likely require dichotomization into White vs. Minority for randomization. We will not allow physician racial category counts to differ by more than two for any one category across arms.
 - d. Mean physician opioid prescription rate may not differ by more than 0.5 standard deviation units across study arms.
 - e. Mean number of orange or red zone shifts may not differ by more than 0.25 across study arms.
- 4) Of the possible allocation schemes meeting the criteria outlined in Step 3, randomly select one for implementation in the study.

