- 2) **Patient-Reported Opioid Use** at three months. This will be collected using a customized instrument assessing whether participants have taken any opioid medication in the last 24 hours. The 24-hour timeframe was selected to maximize accuracy in patient recall and has been used previously. In brief, opioid medications are listed by brand and generic names; a “yes” response to any medication triggers an additional query asking the participant to specify the medication dose (e.g., oxycodone 10mg) and quantity (e.g., four pills), allowing for standardization by morphine milligram equivalents (MME). We anticipate treating this variable as either count or a binary (any dose vs. none), or continuous (MME) for analyses.

Exploratory Outcomes

We expect the following outcomes to be related to the primary and the major secondary outcomes of interest. We deem the more exploratory in nature, and they thus carry less weight in analyses and overall inferences regarding efficacy of intervention.

- 1) **Opioid Prescription Filling** will be queried in the state prescription monitoring database. We anticipate treating this variable as count, binary, or continuous (MME).
- 2) **Patient-Reported Prescription Analgesic Use** in the last 24 hours will be collected using the same customized instrument described above for opioid use. Prescription analgesics include: opioids, benzodiazepines, skeletal muscle relaxants, and gabapentinoids. We anticipate treating this variable as either count or binary.
- 3) **Prescription Analgesic Filling** will be queried in the state prescription monitoring database. Prescription analgesics include: opioids, benzodiazepines, skeletal muscle relaxants, and gabapentinoids. We anticipate treating this variable as either count or binary.
- 4) **Numeric Pain Rating Scale (NPRS)** measures pain intensity from 0 to 10 and is easily understood by laypersons, clinicians, and researchers. We will assess a single item relating to average pain intensity over the last 24 hours. We plan to treat this as a continuous outcome, but we anticipate requiring transformation or nonparametric analyses, as this variable will likely be skewed and exhibit flooring / ceiling effects.

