6. STATISTICAL METHODS

We plan to use descriptive statistics to summarize baseline patient and physician-level variables both overall and by arm. We will use mean±standard deviation (or median and interquartile range [IQR] as appropriate) for continuous variables and frequency / percentage for categorical variables. Specifically, we will summarize age, sex, Keele STarT score, baseline patient-reported outcome scores (PROMIS-PI and ODI), analgesic medication prescription at ED discharge, and the variables listed above. Analyses will involve normal theory methods in general, and in cases of violations of assumptions, we will consider transformation and / or nonparametric / exact methods as appropriate.

Analyses will assume a two-sided 5% significance level. All primary efficacy and safety analyses will be pre-specified as outlined in this SAP, and deviations from planned analyses or post hoc analyses will be labeled as such in any reports or dissemination materials. We do not plan to control for multiple hypothesis tests.

In analyses for each outcome, we plan to control for the respective outcome value at baseline (i.e., in an analysis of covariance [ANCOVA] approach). Analyses for the primary outcome (Y) will involve a linear mixed model (LMM) with repeated measures with fixed effects for: study arm, baseline outcome score (Y0), timepoint, timepoint-by-arm interaction, and known influential predictor effects (age, sex, Keele STarT score). Inference will focus on treatment impacts for the outcome at three months. We will include a random physician effect to account for both within and between physician variability and also to allow for estimation of the intra-cluster correlation coefficient (ICC). The repeated measures on the same participant over time will also introduce a correlation structure across time points, providing the justification for modeling the correlation structure at the

participant level over time. We will use an unstructured correlation matrix to account for the repeated measures within a participant as this has the least assumptions. If the model does not converge or parameters cannot be estimated under this unstructured covariance pattern, we will explore simpler covariance patterns using residual estimated maximum likelihood (REML) comparisons. Including repeated measures per participant will allow us to make most use of all participant data after baseline. We will use assume an unstructured covariance across time.

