
throughout the course of the trial, and we will seek advice from the External Advisory Board and DSMB as we make any interim decisions on stopping enrollment prior to the planned 360 participants.

ICC	Physicians (Total)	Physician % Dropout	Average N participants per Physician	Participant % Dropout	Power: Mean 3.5-point Difference
0.01	40	0	9	0	97%
	40	0	8	5 to 10	95%
	40	0	7	15 to 20	92%
	38	5	9	0	96%
	38	5	8	5 to 10	94%
	38	5	7	15 to 20	90%
	36	10	9	0	95%
	36	10	8	5 to 10	92%
	36	10	7	15 to 20	89%
	34	15	9	0	94%
	34	15	8	5 to 10	91%
	34	15	7	15 to 20	87%
	32	20	9	0	92%
	32	20	8	5 to 10	89%
	32	20	7	15 to 20	85%
	40	0	9	0	96%
	40	0	8	5 to 10	94%
	40	0	7	15 to 20	91%
0.05	38	5	9	0	95%
	38	5	8	5 to 10	93%
	38	5	7	15 to 20	90%
	36	10	9	0	94%
	36	10	8	5 to 10	91%
	36	10	7	15 to 20	88%
	34	15	9	0	93%
	34	15	8	5 to 10	90%
	34	15	7	15 to 20	86%
	32	20	9	0	91%
	32	20	8	5 to 10	88%
	32	20	7	15 to 20	84%
	40	0	9	0	96%
	40	0	8	5 to 10	94%
	40	0	7	15 to 20	91%
	38	5	9	0	95%
0.10	38	5	8	5 to 10	93%
	38	5	7	15 to 20	90%
	36	10	9	0	94%
	36	10	8	5 to 10	92%
	36	10	7	15 to 20	88%
	34	15	9	0	93%
	34	15	8	5 to 10	90%
	34	15	7	15 to 20	86%
	32	20	9	0	91%

32	20	8	5 to 10	88%
32	20	7	15 to 20	84%

We will not need to adjust sample size calculations for the covariate-constrained randomization approach, as this merely controls imbalances across arms on physician-level (i.e. cluster) covariates, such as physician productivity (e.g., patients seen per hour) while preserving the 1:1 study arm allocation ratio. Therefore, controlling imbalance on these physician-level covariates is intended to translate to both equal allocation of physician participant numbers and comparable participant-level covariate distributions across arms. As mentioned above, we anticipate that this increased control over imbalance coupled with the analytic strategies will increase precision and reduce bias in estimating intervention effects. Since the amount of increased precision is unknown, we deem the sample size and power calculations conservative.

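### Physician opioid prescription rate is constrained at randomization, only loosely, but no opioid model adjusts for it; adding it as a covariate is a cheap improvement of uncertain size.

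*SAP*

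**What the plan says.** SAP Section 5 names opioid prescription rate as one of five physician characteristics to be balanced. The allocation is fixed by "We plan for equal allocation (1:1) of physicians across study arms", with 40 physicians in total. Candidate schemes come from "Enumerating a 10 thousand possible allocation schemes at the 1:1 physician allocation ratio", and step 3d retains only those meeting this condition: "Mean physician opioid prescription rate may not differ by more than 0.5 standard deviation units across study arms". Section 5 adds that "the distribution of these physician-level variables may require modification(s) to these thresholds", but the revision history of version 2.0 records no such change.

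Section 6 gives the fixed effects of the primary model as arm, baseline outcome, time, time by arm, and "known influential predictor effects (age, sex, Keele STarT score". Other outcomes follow the same strategy, with generalized linear mixed models for binary and count data. The moderator models contain baseline outcome, arm, moderator and interaction. Section 3 lists the same three adjustment covariates, all at patient level.

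The opioid outcomes are patient-reported use in the last 24 hours at three months (secondary, and named in Aim 2) and prescription filling (exploratory), which "will be queried in the state prescription monitoring database. We anticipate treating this variable as count, binary, or continuous (MME". Prescription analgesic filling is a further exploratory outcome.

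**The concern.** The design treats physician prescribing habit as important enough to constrain, and the analysis then leaves it out. That would matter little if the constraint made the arms nearly equal on it, but a limit of 0.5 SD is wide for 20 against 20 physicians. A sizeable chance difference in prescribing habit can pass, and no term in the opioid models absorbs it.

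The outcomes at stake are those most likely to depend on who treated the patient. Filling can reflect directly what the index physician wrote. Self-reported use three months later may do so to a lesser degree. The patient's own baseline opioid use, which is in the models, does not measure the physician's habit.

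**Working it through.** **The plan's own figure.** Section 5 states "With 40 total physicians, there are over 137 billion ways (40 choose 20) in which we can achieve equal allocation of physicians across study arms". C(40,20) = 137,846,528,820, which agrees.

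**Pass rate of step 3d.** Let S be the between-physician SD of the rate. The SAP does not define its SD unit, so this reading is assumed. Under plain 1:1 allocation the difference in arm means has

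SD = S × sqrt(1/20 + 1/20) = 0.316 S.

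The limit is 0.5/0.316 = 1.58 standard errors, so the share passing is 2Φ(1.58) − 1 = 0.886. Random 20/20 splits gave 88-89% for normal, uniform and moderately skewed rates, and 88-97% for strongly skewed ones.

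**What the limit achieves.** For a normal variable truncated at c = 1.58, the variance is multiplied by 1 − 2cφ(c)/0.886 = 1 − 2 × 1.58 × 0.114/0.886 = 0.59. The variance therefore falls by about 41%, and the SD of the arm difference becomes 0.316 × sqrt(0.59) = 0.243 (0.246 in the random splits).

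**What remains.** The share of all allocations within 0.25 SD is 0.571. Among accepted allocations, the share beyond 0.25 SD is (0.886 − 0.571)/0.886 = 0.36.

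**The other four limits.** Under assumed covariate distributions, all five limits together admit roughly 6-10% of schemes. If the variables are uncorrelated, step 3d still passes about 89% of the schemes that meet the other four, and the SD of the arm difference stays near 0.245. If rate and experience correlate at 0.5, the SD is about 0.23. The other limits therefore do little for this variable unless they correlate with it.

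**Effect on an opioid estimate.** The SAP gives no opioid ICC, no event rate and no link between physician rate and patient outcome. Assumed here: 40 physicians × 9 patients, event rate 30% (p(1−p) = 0.21) and a 12-point true reduction.

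- Among accepted allocations beyond 0.25 SD, the mean absolute difference is 0.316 × (φ(0.79) − φ(1.58))/(Φ(1.58) − Φ(0.79)) = 0.316 × 0.178/0.158 = 0.356 SD.
- If a share R² of the physician variance is explained by the rate, the slope per SD is sqrt(ICC × 0.21 × R²), and the shift is 0.356 times that slope.
- Power was simulated with physician-level linear regression, with and without the rate.

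| ICC | R² | Slope (points per SD) | Shift (points) | Power without → with the rate |
|---|---|---|---|---|
| 0.01 | 10% | 1.4 | 0.5 | no material change |
| 0.01 | 36% | 2.7 | 1.0 | 71% → 71% |
| 0.04 | 36% | 5.5 | 2.0 | 61% → 65% |
| 0.05 | 36% | 6.1 | 2.2 | 57% → 62% |
| 0.10 | 50% | 10.2 | 3.6 | 45% → 55% |
| 0.20 | 64% | 16.4 | 5.8 | 29% → 45% |

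The formula is linear. Simulated shifts are about 0.3-2 points for the low-ICC cases and about 2, 3.5 and 5 points for the last three rows. Adjustment brings them to about zero. For scale, the standard error sqrt(2 × 0.21 × (1 + 8 × ICC)/180) is 5.0 points at ICC 0.01 and 5.5 at ICC 0.04.

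**Type I error.** In the last three settings the nominal 5% test without the rate rejected 4.6%, 3.5% and 3.0% of null trials. With the rate it rejected 4.6-4.8%. Constraining on a prognostic variable and then omitting it makes the test conservative.

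**The case against.** Several stronger readings are tempting, and the SAP does not support them.

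- *The constraint does almost nothing.* The 89% suggests this, but the limit cuts the variance of the arm difference by about 41% and excludes every difference above 0.5 SD.
- *The opioid results are biased.* The imbalance is due to chance, so there is no bias in expectation. While the random physician effect is kept, the imbalance is reflected in the standard error. The shifts above are conditional on allocations more than 0.25 SD apart.
- *Section 6 contradicts itself on baseline adjustment.* Its rule concerns the baseline value of the outcome, which for patient-reported use is the patient's own value. A physician's past prescribing rate is a different variable on a different unit.
- *Section 8 overclaims.* It says "we anticipate that this increased control over imbalance coupled with the analytic strategies will increase precision and reduce bias in estimating intervention effects". That is general, puts no number on balance for this variable, and serves only to justify leaving the sample size unadjusted.
- *The achieved imbalance will go unreported.* Section 6 already summarizes physician-level variables by arm.

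Three further objections concern size, and all three stand. Enrolment is complete, so the arm difference is now a fixed number; the team can know it and a reader of the SAP cannot, and it may be near zero. The only ICC evidence in the SAP is 0.01-0.04 from pilot work, with 0.10 called conservative, both in the PROMIS-PI power section. At those pilot values the gain is small. Finally, the mechanism is strongest for filling, which is exploratory, and the simulated power comes from a linear physician-level regression rather than the planned mixed model.

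What the objection does not remove is that the variable is already held, was judged important enough to constrain, and is absent from every opioid model. Including it showed no measurable loss of power even in the weakest case simulated.

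**Conclusion.** The point holds as a recommended refinement of the opioid analyses, not as an error or contradiction in the SAP. Two facts are firm: step 3d alone passes 88.6% of 20-against-20 allocations, and no opioid model contains the physician's prescription rate.

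The benefit of adding it is uncertain. Under the stated assumptions, the power gain is about 0-4 points at ICC 0.01-0.04 with 10-36% of physician variance explained, and about 5-17 points at ICC 0.05-0.20 with 36-64% explained. The corresponding shifts, in allocations more than 0.25 SD apart, are about 0.3-2 and 2-5 percentage points. The benefit is probably larger for filling than for self-reported 24-hour use at Month 3. A reader might extend the point to the PROMIS-PI analysis, but nothing in this argument bears on the validity of that test.

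**What to change.** Add one sentence to SAP Section 6: the models for patient-reported opioid use and for opioid and analgesic prescription filling include the physician's baseline opioid prescription rate, as used at randomization and kept continuous, as a fixed effect. Enter it in the revision history as a dated change made before database lock. If it comes later, label it as a deviation under the SAP's own rule in Section 6.

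The allocation, the limits in Section 5, the PROMIS-PI model and Section 8 need no change. The cost is one physician-level degree of freedom out of about 38 (40 physicians less two arm means). No new data are needed, because the rate was required for the randomization.

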6. STATISTICAL METHODS

We plan to use descriptive statistics to summarize baseline patient and physician-level variables both overall and by arm. We will use mean±standard deviation (or median and interquartile range [IQR] as appropriate) for continuous variables and frequency / percentage for categorical variables. Specifically, we will summarize age, sex, Keele STarT score, baseline patient-reported outcome scores (PROMIS-PI and ODI), analgesic medication prescription at ED discharge, and the variables listed above. Analyses will involve normal theory methods in general, and in cases of violations of assumptions, we will consider transformation and / or nonparametric / exact methods as appropriate.

Analyses will assume a two-sided 5% significance level. All primary efficacy and safety analyses will be pre-specified as outlined in this SAP, and deviations from planned analyses or post hoc analyses will be labeled as such in any reports or dissemination materials. We do not plan to control for multiple hypothesis tests.

In analyses for each outcome, we plan to control for the respective outcome value at baseline (i.e., in an analysis of covariance [ANCOVA] approach). Analyses for the primary outcome (Y) will involve a linear mixed model (LMM) with repeated measures with fixed effects for: study arm, baseline outcome score (Y0), timepoint, timepoint-by-arm interaction, and known influential predictor effects (age, sex, Keele STarT score). Inference will focus on treatment impacts for the outcome at three months. We will include a random physician effect to account for both within and between physician variability and also to allow for estimation of the intra-cluster correlation coefficient (ICC). The repeated measures on the same participant over time will also introduce a correlation structure across time points, providing the justification for modeling the correlation structure at the

participant level over time. We will use an unstructured correlation matrix to account for the repeated measures within a participant as this has the least assumptions. If the model does not converge or parameters cannot be estimated under this unstructured covariance pattern, we will explore simpler covariance patterns using residual estimated maximum likelihood (REML) comparisons. Including repeated measures per participant will allow us to make most use of all participant data after baseline. We will use assume an unstructured covariance across time.

To evaluate efficacy, the Wald model type III test for fixed arm effect will be evaluated assuming a two-sided 5% type I error rate. The primary contrast of interest to address the primary research aims involves the comparison of the model-estimated mean outcome score at three months (T4) across study arms. This modeling strategy is robust to unbalanced (i.e., incomplete) data across study time points. We will also provide results for unadjusted analyses (i.e., without accounting for the pre-specified covariates). Analyses of additional outcomes will follow the same general analytic strategy: LMM with fixed arm, baseline outcome value, influential baseline covariate effects, and a random physician effect and covariance patterns to account for repeated measures within participants. We chose to incorporate baseline outcome as a covariate in the model, rather than as a time point, based on clinical reasoning. As these baseline values (e.g., PROMIS-PI score at the index ED visit) are assessed pre-intervention and primary analyses aim to assess outcome(s) as follow-up accounting for pre-intervention state. Incorporating this baseline value in the analytic model as a fixed effect will increase precision and reduce bias on the intervention effect estimate for primary outcome at the time point of interest as the baseline value will likely be highly correlated with outcome at follow-up (previous data: $p < 0.001$ for both PROMIS and ODI).

Residual diagnostics will assess model fit and assumptions, and in the case of violation, we will explore transformations / nonparametric methods as indicated above. In the event of poor model fit, we may explore different distributional assumptions as appropriate (e.g., Poisson for count or rate data) with the corresponding canonical link (e.g., log) function. As above, we will assess model fit via residual diagnostics and may consider transforming or nonparametric methods as needed.

Analyses for outcomes that are either binary or count will follow the same general approach as above; however, they will involve generalized linear mixed effects (GLMMs) models with the appropriate distributional (e.g., binomial or Poisson) and link (e.g., logit or log) assumptions. Modeling the covariance structure for these outcomes may result in unstable model estimates. If this occurs, we anticipate removing the random physician effect and including a random participant effect instead to account for correlation.

Exploratory Analyses

In addition to repeating the above analyses with exploratory outcomes, we will conduct exploratory analyses to study effects among subgroups of patients (moderator analyses) and examine the potential impact of PT use among patients in the control arm.

Planned moderator analyses will include the following moderators:

1. Opioid naivete as measured by whether patients report taking opioids within the last 24 hours at their index ED visit or have a history of opioid prescription filling in the Illinois prescription monitoring program within the last 3 months.
2. Initial symptom burden measured as “moderate/severe” if their baseline measures of PROMIS pain scores are ≥ 60 or their STarT score registers as “high risk,” defined as a subscore ≥ 4 (questions 5-9).
3. Age ≥ 65 years old
4. Primary treatment classification, as per the clinical care protocol (directional preference, traction, stabilization, manipulation, nociplastic presentation). As primary treatment classification is assigned only in those participants in the treatment arm (NEED-PT), we will use two approaches to study the effects of treatment classification. First, we will modify GLMM to include treatment classification effects (as opposed to just a study arm effect). Second, we will use matching methods (e.g., propensity score matching or augmented synthetic controls) to match individuals in the NEED-PT arm who have a given primary treatment classification to control arm participants on baseline covariates. We would then use GLMM to estimate the impact of each treatment classification separately.

Analyses will focus on PROMIS-PI scores measured three months after patients’ index visits, as well as ODI scores and opioid use (proportion using an opioid within the last 24 hours) at the same time point. Analyses will involve generalized linear models with appropriate link functions (identity for PROMIS-PI and logit for opioid

use) that include fixed effects for baseline measures of the outcome of interest, treatment assignment, a moderator variable, and a treatment-moderator interaction. As above, PROMIS-PI will be modeled with standard normality assumptions, which will be evaluated via residual diagnostics and appropriate transformations will be used as necessary. Separate models will be fit for each outcome and moderator. Tests for the treatment-moderator interaction will be two-sided with a 5% type I error rate, and we will report point estimates and 95% confidence intervals. For the logistic regression involving opioid use, we will use Wald confidence intervals and Wald tests. We will not make multiple comparison adjustments.

Mediation analyses will focus on PCS and PSEQ as possible mediators. Our hypotheses are that embedding a PT in the ED can impact patients downstream pain catastrophizing and self-efficacy which will in turn lead to lower reported pain and less frequent opioid use. Our key dependent variables will be PROMIS-PI and opioid use at three months after the index visit. PCS and PSEQ measured at one month will be the mediators of interest. We will use a nonparametric approach to analyses, running separate models for each outcome and mediator (5). In addition, we will examine the possible correlation between mechanisms by using a joint nonparametric estimation framework (6).

In addition, we will conduct a complier analysis. Based on pilot data, we expect some patients in the control arm will receive a discretionary PT consultation as part of usual care. These consultations will be operationally different from those in the treatment group, as the PT will not be embedded with the care teams in the control arm. Conversely, it is possible some treatment arm patients may not receive an embedded PT consult, though we expect this will be rarer. Since we hypothesize that PT consultation will play a large role in this intervention's effectiveness, we propose to examine the impact of these differential PT consultations (discretionary, embedded) in two ways. First, we will re-create the proposed confirmatory analyses excluding control patients receiving a PT consultation and intervention arm patients who do not. Second, we will use a generalized mediation analysis that includes all patients that treats receipt of a PT consult as a mediator to estimate the direct and indirect effects of treatment assignment and PT consultation. This mediation analysis will focus on PROMIS-PI at three months post-index visit as the outcome of interest, and use a generalized nonparametric estimation approach (5).

